**STUDY SUMMARY (DRUGS)**

TITLE	A Randomized, Double-Blinded, Placebo-Controlled Study to Determine if Caffeine Citrate (caffeine) Accelerates Emergence from Anesthesia
OBJECTIVES	To determine if caffeine will accelerate emergence from anesthesia.
PRIMARY OBJECTIVE	Determine whether subjects wake more rapidly from anesthesia after administration of caffeine as measured by the time between terminating anesthetic and the reinstatement of the gag reflex.
SECONDARY OBJECTIVES	Determine whether subjects wake more rapidly from anesthesia after administration of caffeine as measured by the time between terminating anesthetic and responding to simple commands (“squeeze my hand”).  Normally patients show cognitive impairments for hours after waking from anesthesia. We wish to determine whether caffeine administration ameliorates the cognitive impairment.
STUDY CENTER(S)	Single-center at University of Chicago
NUMBER OF SUBJECTS	Up to 8
DIAGNOSIS AND MAIN INCLUSION CRITERIA	Healthy male, ages 25-40 with no systematic diseases or conditions, metabolic equivalents of functional capacity, low risk for Obstructive Sleep Apnea, no history of arrhythmia, BMI < 30 kg/m  , no personal or family history of malignant hyperthermia, no history of any mental illness, no history of drugs or alcohol abuse, no history of seizure disorders or head trauma
DURATION OF SUBJECT PARTICIPATION AND DURATION OF STUDY	Subjects will be on study for up to 10 weeks
INVESTIGATIONAL PRODUCT	Caffeine Citrate
DOSE, ROUTE, REGIMEN	15 mg/kg body weight, given intravenously 10 min before the end of 1 hour isoflurane anesthesia

DURATION OF ADMINISTRATION	Study drug given intravenously across a 10 min time window
STATISTICAL METHODOLOGY	In this crossover study volunteers will serve as their own controls. The data will be analyzed with a paired t-test.

LIST OF ABBREVIATIONS

*EXAMPLES*

UCMC	UNIVERSITY OF CHICAGO MEDICAL CENTER
UC	UNIVERSITY OF CHICAGO
OCR	OFFICE OF CLINICAL RESEARCH
IRB	INSTITUTIONAL REVIEW BOARD
URA	UNIVERSITY RESEARCH ADMINISTRATION
ORS	OFFICE OF RESEARCH SERVICES
CRSO	CLINICAL RESEARCH SUPPORT OFFICE
UCCRC	UNIVERSITY OF CHICAGO CANCER CLINICAL RESEARCH CENTER
CRC	CLINICAL RESOURCE CENTER (FORMERLY GCRC)
DSMB	DATA SAFETY AND MONITORING BOARD
FDA	FOOD AND DRUG ADMINISTRATION
CDER	CENTER FOR DRUG EVALUATION AND RESEARCH
CBER	CENTER FOR BIOLOGICS EVALUATION AND RESEARCH
NIH	NATIONAL INSTITUTES OF HEALTH
NCI	NATIONAL CANCER INSTITUTE
CTSA	CLINICAL AND TRANSLATIONAL SCIENCE AWARD
ITM	INSTITUTE FOR TRANSLATIONAL MEDICINE

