### **2.3 Schedule of Events**

Each subject will attend 3 sessions to complete the study. In the first session, an anesthesiologist will explain the purpose of the trial and carefully go over the consent form. If the subject is willing to enroll the consent form will be signed. Then the anesthesiologist will take a detailed medical history and perform a physical examination of the subject. A baseline EKG and urine toxicology screen text will be obtained. If the subject meets the criteria for the study, the subject will be enrolled in the trial. At this point a pre-study training session will be provided to familiarize the subject with the psychomotor tests. In the following two sessions, each subject will receive general anesthesia in one session (with a saline injection as a placebo control) and receive general anesthesia plus an injection containing caffeine citrate (15 mg/ kg) in the other session in a randomized manner. For each subject, each session involving anesthesia will be at least 2 weeks apart. Detailed study procedure will be described in section 5 below.

**Please Note:** We will try to process two subjects on a single anesthesia day. One at 7:00 AM and another at 1:00 PM. In the Pilot study we tested one subject per day. The subjects arrived at UC at 7:00 AM and the entire anesthesia procedure including recovery was finished by 11:00 AM. That was wasteful, in terms of time. Normally anesthesiologists put multiple people to sleep per day. They don't finish their days at 11:00 AM. That is why we would like to have one subject in the morning and a second subject in the afternoon.

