study drug (caffeine citrate) or the placebo (saline) will be given intravenously 10 min before the end of 1 hour isoflurane anesthesia. The anesthesiologists will be blinded to the medication injected to the subject since the pharmacists in the IDS GROUP prepare the drug or the placebo control. When isoflurane is turned off, the subject will eliminate isoflurane passively via breathing. We will measure the time between when the isoflurane is stopped to the awakening of the subject. We will record the time to recovery of the gag reflex, until the subject's eyes open, until the subject's mouth opens, and the time until the subject can respond to the command to grip the hand of the attending physician and the removal of the laryngeal mask. After the subject is awake and relatively alert, he will perform psychomotor tests to measure his cognitive function. The subject will be required to complete a simple set of cognitive tests to determine if they are still impaired by anesthetic. Both "control" and test subjects will be required to complete the same tests. In total there are 3 different tests. The tests will be repeated every 15 minutes in order to obtain a recovery time course.

There will be at least two anesthesiologists present during the entire period of anesthesia. Each subject will be given a dose of antiemetic medication, zofran (4 mg) 20 minutes before the end of the anesthesia to minimize the incidence of post anesthesia nausea and vomiting. During the period of anesthesia, we will keep the subject's BP within 20% of its pre-anesthesia value. If the BP falls more than 20% of the baseline, for more than 5 minutes, we will first give IV fluid to replete the fluid deficit due to the restriction of fluid intake prior to the study. Vasoactive medications will be given if necessary.

One hour after the isoflurane is stopped, if the subject is awake, oriented and showing stable vital signs, one of the anesthesiologists may leave the room to prepare for the afternoon session. There will always be at least one anesthesiologist with the test subject at all times. Most of the time there will be two anesthesiologists.

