## 6.2 Statistical Methods

We hope to use a simple paired t-test to analyze the data, using volunteers as their own controls.

Crossover study - Each volunteer receives anesthesia 2 times: once without drug (control) and once with caffeine (test). Our animal studies suggest that variance is dramatically minimized when test subjects can be used as their own controls, in this manner. If humans recapitulate the rodent studies then 8 volunteers should provide an adequately

sized sample to answer the research question. The study was originally divided into two parts. The first part, the Pilot study has been completed.

Part 1: In order to demonstrate feasibility and safety, we carried out a pilot study of 2 healthy human volunteers to assess whether caffeine aids these subjects in recovering from isoflurane anesthesia. Recovery times were measured in three ways: as the time between the time when anesthetic is terminated until the subject starts to gag, can open his eyes, and the subject is able to respond to simple commands (like squeeze the clinician's hand). Each of the three endpoints was monitored and plotted separately. In this pilot study caffeine citrate (caffeine) was used at 10 mg/kg. By comparing subjects that wake from anesthesia who are injected with a saline solution to subjects that are injected with caffeine we were able to show that caffeine is as efficient in humans as in rodents. Now that we have demonstrated safety and feasibility, if the IRB gives us permission, we will continue to Part 2 of our study. Time from the end of anesthesia to eye opening will be analyzed, as will be the time from the end of anesthesia to response to a simple command. Each parameter (gagging, eye opening and response to command) will be analyzed and plotted separately.

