There are cognitive impairments that last for hours following anesthesia (Nathanson *et al.*, 1995; Larsen *et al.*, 2000; Chen *et al.*, 2001). Reaction times and memory are impaired following anesthesia (Nathanson *et al.*, 1995; Larsen *et al.*, 2000; Chen *et al.*, 2001). Outpatients are being released from surgery/ anesthesia on an ever shortening time scale to save money. It would be significant if clinicians could wake the patients safely, rapidly and completely with no cognitive issues. The psychomotor studies will allow us to assess whether caffeine helps ameliorate the cognitive problems associated with anesthesia. Subjects will be required to carry out a series of simple psychomotor tests thirty minutes after anesthesia and then again two hours later. By comparing results, memory and reaction times we will determine whether Caffeine helps ameliorate cognitive problems, relative to the saline treated controls. Data from each test will be analyzed and plotted separately.

Part 2: Up to 8 additional healthy human males will be recruited for this part of the study. If the effects of caffeine in humans mirror that of the rat, we will need ~8 more volunteers to complete the trial assuming that each volunteer attends all 4 anesthesia sessions. We anticipate some dropout. This is the part we are asking for permission to start.

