### **6.3 Subject Population(s) for Analysis**

The data from all subjects will be analyzed without knowledge of whether the data comes from a control or test condition. After breaking the code, data will be grouped accordingly. All data will be analyzed in two different ways. Using a paired t-test data from subjects that have completed the two anesthesia sessions of the study will be analyzed and plotted. Separately, using an unpaired t-test all data will be grouped together including that from subjects who did not finish the trial. In this way the data will be compared. Only data from subjects that failed the toxicology screen will be excluded.

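### The cognitive endpoints of the crossover are tested with no period term, so a practice gain would cost power when the order is balanced and add bias when it is not

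*Combined protocol and SAP*

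**What the plan says.** The Study Summary gives the design and the test together: "In this crossover study volunteers will serve as their own controls. The data will be analyzed with a paired t-test". Section 6.2 states the method as an intention: "We hope to use a simple paired t-test to analyze the data, using volunteers as their own controls". Section 6.3 applies two analyses to all data. For completers: "Using a paired t-test data from subjects that have completed the two anesthesia sessions of the study will be analyzed and plotted". For everyone: "Separately, using an unpaired t-test all data will be grouped together including that from subjects who did not finish the trial". Section 9.1 mentions only a t-test. No section names a period, sequence or carry-over term. On the psychomotor scores section 6.2 adds only this: "Data from each test will be analyzed and plotted separately".

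On exposure to the tests, section 2.3 (repeated in 5.1) says: "At this point a pre-study training session will be provided to familiarize the subject with the psychomotor tests". Section 5.2 then describes word recall, digit-symbol substitution and time estimation in both anesthesia sessions, which are at least two weeks apart. It says that the digit-symbol codes change at each administration. It does not say whether the 20 words change between sessions.

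The schedule within a session is given in two ways. Section 5.2 says: "The tests will be repeated every 15 minutes in order to obtain a recovery time course". Later in the same section the suite is given once and repeated two hours later, and section 6.2 puts testing "thirty minutes after anesthesia and then again two hours later".

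Section 2.5 assigns order from a random number sequence and states no blocking or balance. Section 2.2 requires 6 to 8 completers, and section 3.13 expects appreciable dropout.

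**The concern.** In a two-period crossover, anything that shifts scores between session 1 and session 2 enters each man's caffeine-minus-saline difference. The sign is positive for men who get caffeine second and negative for men who get it first. Practice on psychomotor tests is an obvious candidate for such a shift. A paired t-test on the pooled differences treats this systematic swing as random scatter. If the two orders are unequal in number, part of it also stays in the treatment estimate.

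At stake is the secondary objective on cognitive recovery. A real effect could be missed although the randomised sequence, known at unblinding, would remove the shift. With an uneven order, practice could be partly credited to caffeine or held against it.

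**Working it through.** **The plan's own figure.** The only sample-size figure (section 6.1) concerns rat waking time. The difference is 540 − 269.67 = 270.33 s, and the pooled SD is √((159.04² + 103.69²)/2) = 134.25 s. At two-sided 0.01 and 95% power, a two-sample noncentral-t calculation gives 11 per condition (power 0.959; 0.976 at 12), close to the stated 12. The documents give no SD, effect or practice gain for the cognitive tests, so what follows is in units of an assumed SD.

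**Model.** Let τ be the treatment effect, π the gain from session 1 to session 2, and s the SD of the within-subject difference with the period effect removed. The difference D has mean τ + π in one order (n_a men) and τ − π in the other (n_b men), with n = n_a + n_b.

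- Bias of the paired estimate: π(n_a − n_b)/n. This is 0 at 4:4, π/4 at 5:3 and π/2 at 6:2.
- Expected sample variance of D: s² + π²·4n_a·n_b/[n(n−1)]. At 4:4 the factor is 64/56 = 8/7, so the variance is multiplied by 1 + (8/7)(π/s)².
- Period-adjusted estimate: the mean of the two sequence means, with standard error (s/2)√(1/n_a + 1/n_b) on n − 2 df. It does not depend on π.

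**Balanced order, 4:4, assumed τ = 1.5 SD.** Plain-test results come from simulation with at least 200,000 trials per setting. Adjusted power is from the noncentral t.

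| Assumed gain π/s | SE multiplier, plain test | Type I error, nominal 0.05 | Power at 0.05, plain / adjusted | Power at 0.01, plain / adjusted |
|---|---|---|---|---|
| 0 | 1.00 | 5.0% | 95 / 94% | 74 / 69% |
| 0.25 | 1.035 | 4.4% | 94 / 94% | 71 / 69% |
| 0.5 | 1.13 | 3.0% | 91 / 94% | 62 / 69% |
| 1 | 1.46 | 0.7% | 75 / 94% | 32 / 69% |

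The two tests break even near 0.3 SD at both levels. With a smaller assumed effect of 1.2 SD at 0.05, the plain test gives 83, 81, 75 and 51% over the same gains, against 81% adjusted. With six completers at 3:3 and τ = 1.5 SD, gains of 0.5 and 1 SD give 75 and 50%, against 78% adjusted.

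**Uneven order.** If each order is an independent fair draw (an assumption, because section 2.5 does not say), exact 4:4 has probability 70/256 = 0.27, and 6:2 or worse has probability 2(28 + 8 + 1)/256 = 0.29. At 6:2 with a 1 SD gain the plain estimate is off by 0.5 SD and the nominal 5% test rejects about 8.5% of the time under the null. At 5:3 the estimate is off by 0.25 SD, but the extra variance outweighs this and type I error is about 2%. The adjusted test holds 5% throughout.

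**Price of adjusting when π = 0, τ = 1.5 SD (noncentral t).**

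| Split | Power at 0.05, plain → adjusted | Power at 0.01, plain → adjusted |
|---|---|---|
| 4:4 | 95 → 94% | 74 → 69% |
| 5:3 | 95 → 92% | 74 → 65% |
| 6:2 | 95 → 86% | 74 → 54% |
| 3:3 | 83 → 78% | 47 → 38% |

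**The case against.** The plan does act against practice. The training session comes before either measured session, so some learning happens before it can matter, and changing the digit-symbol codes is aimed at item learning. No feedback is described for the time estimate, so a gain there is conjecture. The practice gain and the effect size are both assumed. Below about 0.3 SD the plain test is as good or slightly better, and at an uneven split the adjusted test gives up real power. The endpoint is secondary and was not powered. All of this stands and keeps the point small. It does not remove it: nothing shows that training and new codes take the gain to zero, and the code change covers only one of the tests.

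Three stronger readings are tempting:

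- A reader might infer that the paired t-test produces false positives in general. With balanced order it does the reverse; inflation needs a split such as 6:2.
- A reader might take the 15-minute schedule as settled and conclude that practice must be heavy. The same section and section 6.2 describe two time points, so the documents do not support that.
- A reader might extend the criticism to the primary analysis or the sample size. Waking time is not a learned test score, and the sizing in section 6.1 does not depend on this point.

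**Conclusion.** The concern holds as a minor matter of efficiency and protection against bias. The named analyses ignore period in a design where a period effect on the cognitive scores is plausible but not quantified. At 4:4 the consequence is only lost power: nothing below a gain of about 0.3 SD, about 3 points at 0.5 SD and about 20 at 1 SD (at 0.05, effect 1.5 SD). With an uneven order, which the plan does not rule out, the paired estimate is biased as well. These sizes rest on the assumed effect, the assumed gain, two-sided testing and, for the chance of imbalance, independent fair draws.

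**What to change.** For the psychomotor scores, pre-specify the standard 2x2 crossover analysis: the mean of the two sequence means of the caffeine-minus-saline differences, or equivalently for completers a model with treatment, period and subject. Report the estimated period effect and show the plain paired t-test alongside. For waking times, give the period-adjusted model as a sensitivity analysis. Fix this before unblinding, so that the choice of model cannot follow the results. Reconcile the two test schedules (section 5.2 internally, and with section 6.2), because the schedule determines which scores are compared.

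The cost is wording only: no new data, subjects or procedures. The statistical price is one degree of freedom plus, with uneven orders, a larger standard error. If there is no practice effect, that is about 1 power point at 0.05 and 5 at 0.01 for 4:4, rising to about 9 and 20 for 6:2.

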## 1. INTRODUCTION

### 1.1 BACKGROUND AND RATIONALE

#### 1.1.1 Background: Disease and current understanding of disease

Our lab has studied anesthetics for almost fifteen years. We, as well as other labs, found that anesthetics inhibit neurotransmitter release (Crowder *et al.*; van Swinderen *et al.*, 1999; Winegar & MacIver, 2006; Herring *et al.*, 2009; Herring *et al.*, 2011; Saifee *et al.*). We thought that if we could reverse this action that we would be able to reverse aspects of anesthesia. In our preliminary studies, several drugs were studied that normally facilitate neurotransmitter release. If inhibiting neurotransmitter release is part of the mechanism leading to anesthesia (Crowder *et al.*; van Swinderen *et al.*, 1999; Winegar & MacIver, 2006; Herring *et al.*, 2009; Herring *et al.*, 2011; Saifee *et al.*) then drugs that facilitate neurotransmitter release may aid in reversing anesthesia. Elevating intracellular cAMP, with drugs like forskolin or caffeine, is well known to facilitate neurotransmitter release (Byrne & Kandel, 1996; Trudeau *et al.*, 1996; Fujita-Yoshigaki, 1998; Fujita-Yoshigaki *et al.*, 1998; Lonart *et al.*, 1998; Trudeau *et al.*, 1998; Takahashi *et al.*, 1999; Trudeau *et al.*, 1999; Kuromi & Kidokoro, 2000; Hilfiker *et al.*, 2001; Machado *et al.*, 2001; Sakaba & Neher, 2001; Burgoyne & Morgan, 2003; Kuromi & Kidokoro, 2003; Lonart *et al.*, 2003; Sakaba & Neher, 2003; Seino & Shibasaki, 2005; Kasai *et al.*). We found that drugs that elevate intracellular cAMP levels reversed the inhibition of neurotransmitter release caused by anesthetics in *in vitro* studies. In addition, the cAMP elevating drugs caused rats to wake up very quickly from anesthesia.

Normally recovery from anesthesia is passive. Anesthetic is terminated and people wake up. Some do so slowly. Age, genetics, gender and other factors come into play with regards to waking time (Solt *et al.*, 2011). But currently there is nothing that a clinician can do to hurry the process. Additionally, there are cognitive impairments that last for hours following anesthesia (Nathanson *et al.*, 1995; Larsen *et al.*, 2000; Chen *et al.*, 2001). Reaction times and memory are impaired following anesthesia (Nathanson *et al.*, 1995; Larsen *et al.*, 2000; Chen *et al.*, 2001). People (outpatients) are being released from surgery/ anesthesia on an ever shortening time scale to save money. It would be significant if clinicians could wake the patients safely, rapidly and completely with no cognitive issues.

Anesthesia is thought to work similarly in humans and rodents. In our preliminary studies we found that drugs that elevate intracellular cAMP, like caffeine, dramatically accelerated recovery from anesthesia in rats. *The question that we hope to address is the following: Do drugs that elevate cAMP levels work the same way in humans? Do these drugs accelerate emergence from anesthesia?* Preliminary data from a Pilot study suggests that this is in fact the case.

#### 1.1.2 Investigational Agent

The drug that will be used in this study is caffeine citrate.

In August of 2013 the FDA was sent an application for IND exemption for caffeine. The exemption was not granted. Our next step was to obtain NIH funding for the project, which we obtained. Next we sent off a formal IND application for caffeine citrate. That

IND was approved with (IND #127863). The University of Chicago IRB also approved our protocol (IRB 15-0897).

### 1.1.3 Preclinical data

Previously my lab has shown that clinically relevant concentrations of anesthetics inhibit neurotransmitter release from both secretory cells and neurons. We tested isoflurane, propofol, etomidate and ketamine. All four anesthetics efficiently inhibited neurotransmitter release (Herring BE, [name] Z, Marks J and [name] AP (2009); Herring BE, McMillan, K., Pike, C. Marks, J, [name] AP., [name] Z (2011); [name] Z, McMillan, K., Pike, CM., Cahill, AL., Herring BE., Wang, Q., & [name] AP., (2013)).

We hypothesized that *inhibition of neurotransmitter release plays a key role in how anesthetics produce anesthesia in animals and humans*. Furthermore we hypothesized *that drugs that reverse the inhibitory effects of anesthetics on the release machinery may help accelerate recovery from anesthesia*. Historically, cAMP signaling has been shown to play a key role in synaptic function and plasticity. Elevating cAMP facilitates neurotransmitter release (Byrne & Kandel, 1996; Trudeau *et al.*, 1996; Fujita-Yoshigaki, 1998; Fujita-Yoshigaki *et al.*, 1998; Lonart *et al.*, 1998; Trudeau *et al.*, 1998; Takahashi *et al.*, 1999; Trudeau *et al.*, 1999; Kuromi & Kidokoro, 2000; Hilfiker *et al.*, 2001; Machado *et al.*, 2001; Sakaba & Neher, 2001; Burgoyne & Morgan, 2003; Kuromi & Kidokoro, 2003; Lonart *et al.*, 2003; Sakaba & Neher, 2003; Seino & Shibasaki, 2005; Kasai *et al.*). We posited that elevating intracellular cAMP might alter anesthetic action by restoring neurotransmitter release. Drugs that elevate [cAMP]; levels, were tested; these drugs were found to completely reverse the inhibitory effects of anesthetics on neurotransmitter release in *in vitro* studies. When tested, *these same cAMP elevating drugs dramatically accelerated recovery from anesthesia in rats*. So far we have tested three cAMP elevating drugs (forskolin, theophylline and caffeine) in rats. All accelerate recovery from anesthesia in rats. The Pilot study that was just completed suggests that caffeine appears to accelerate emergence from anesthesia in humans.

There are two studies that bear directly on the cAMP accelerating emergence from anesthesia hypothesis. In the 1970's Cohn et al showed that direct inject of cAMP into the brain reduced the duration of narcosis for a series of sedative, hypnotic, tranquilizer and anesthetic drug tested {Cohn, 1975 #152}. They tested 8 different drugs. It appears that cAMP effectively reduced the waking times for all 8 drugs. More recently, the Solt lab has shown that activation of D1 dopamine receptors accelerates emergence from anesthesia {Taylor, 2013 #68}. D1 receptors are always coupled to the cAMP machinery i.e. activation of this class of receptor always produces an elevation of cAMP in cells that express the receptor.

Some of the preliminary results are shown below:

